5.1.3 Subject Exclusion Criteria

The subject must be excluded from participating in the trial if the subject:

1. Is currently participating in or has participated in a study of an investigational agent or using an investigational device within 4 weeks of the first dose of treatment.
2. Has a diagnosis of immunodeficiency or is receiving systemic steroid therapy or any other form of immunosuppressive therapy within 7 days prior to the first dose of trial treatment. Systemic steroids administered specifically as a premedication for chemotherapy infusion or radiotherapy are allowed.
3. Has had a prior monoclonal antibody within 4 weeks prior to study Day 1 or who has not recovered (i.e., \leq Grade 1 or at baseline) from adverse events due to agents administered more than 4 weeks earlier.
4. Has had prior chemotherapy, targeted small molecule therapy, or radiation therapy within 2 weeks prior to study Day 1 or who has not recovered (i.e., \leq Grade 1 or at baseline) from adverse events due to a previously administered agent.
 - Note: Subjects with \leq Grade 2 neuropathy are an exception to this criterion and may qualify for the study.

- Note: If subject received major surgery, they must have recovered adequately from the toxicity and/or complications from the intervention prior to starting therapy.

5. A history of prior radiotherapy that precludes delivery of hypofractionated radiotherapy
6. Has a known additional malignancy that is progressing or requires active treatment. Exceptions include basal cell carcinoma of the skin, squamous cell carcinoma of the skin, or in situ cervical cancer that has undergone potentially curative therapy.
7. Has known active central nervous system (CNS) metastases and/or carcinomatous meningitis. Subjects with previously treated brain metastases may participate provided they are stable (without evidence of progression by imaging for at least four weeks prior to the first dose of trial treatment and any neurologic symptoms have returned to baseline), have no evidence of new or enlarging brain metastases, and are not using steroids for at least 7 days prior to trial treatment.
8. Has an active autoimmune disease requiring systemic treatment within the past 3 months or a documented history of clinically severe autoimmune disease, or a syndrome that requires systemic steroids or immunosuppressive agents. Subjects with vitiligo or resolved childhood asthma/atopy would be an exception to this rule. Subjects that require intermittent use of bronchodilators or local steroid injections would not be excluded from the study. Subjects with hypothyroidism stable on hormone replacement or Sjogren's syndrome will not be excluded from the study.
9. Has evidence of interstitial lung disease or active, non-infectious pneumonitis.
10. Has an active infection requiring systemic therapy.
11. Has a history or current evidence of any condition, therapy, or laboratory abnormality that might confound the results of the trial, interfere with the subject's participation for the full duration of the trial, or is not in the best interest of the subject to participate, in the opinion of the treating investigator.
12. Has known psychiatric or substance abuse disorders that would interfere with cooperation with the requirements of the trial.
13. Is pregnant or breastfeeding, or expecting to conceive or father children within the projected duration of the trial, starting with the pre-screening or screening visit through 120 days after the last dose of trial treatment.
14. Has a known history of Human Immunodeficiency Virus (HIV) (HIV 1/2 antibodies).
15. Has known active Hepatitis B (e.g., HBsAg reactive) or Hepatitis C (e.g., HCV RNA [qualitative] is detected).

16. Has received a live vaccine within 30 days prior to the first dose of trial treatment.

5.2 Trial Treatments

The treatment to be used in this trial is outlined below in Tables 2 and 3

Table 2 Pembrolizumab Treatment

Drug	Dose/Potency	Dose Frequency	Route of Administration	Regimen/Treatment Period	Use
Pembrolizumab	200 mg	Every 3 weeks	IV infusion	6 three week cycles*	Experimental
The PEMBROLIZUMAB dosing interval may be increased due to toxicity as described in Section 5.2.1.2.					

Pembrolizumab should be administered 7 days (+/- 3 days) prior to the first fraction of hypofractionated radiation.

*NOTE: Patients who have stable or responding disease and are felt to be clinically benefiting from the drug can continue receiving pembrolizumab for up to 2 years. For cancers not currently commercially approved for treatment with pembrolizumab, the drug will be provided by Merck.

In the initial ***Safety Phase***, there will be two cohorts of patients based upon the radiotherapy dose delivered to the index metastatic lesion in the lung, liver, bone or soft tissue:

Cohort 1: 8 Gy x 3 to the index lesion

Cohort 2: 17 Gy x 1 to the index lesion*

*Subjects with locally advanced pancreatic cancer will be enrolled only in the 8 Gy x 3 cohort.

Patients are stratified by prior PD-1 therapy. 24 patients will be enrolled, 12 per stratum and 6 per fractionation cohort within each stratum. Standard safety decision-making will be used. The regimen is safe if no more than 0-1 dose-limiting toxicities (DLT) are observed in 6 patients within a cohort within a stratum. Enrollment in a cohort within a stratum will stop if 2+ DLT are observed within that cohort at any time during the safety phase. If 2+ DLT are observed in Cohort 1 in a stratum, then Cohort 2 within that stratum will still be tested. Cohort 1 → Cohort 2 is **not** an escalation of dose. DLT is defined as any Grade 3 or higher non-hematological toxicity and any Grade 4 hematological toxicity that is probably, possibly or definitely related to the combination of Pembrolizumab and hypofractionated radiotherapy.

Table 3. Hypofractionated Radiotherapy

Safety Phase:

Stratify	Progressed on Prior PD-1 (Melanoma or NSCLC) No Prior PD-1 (Pancreas, Breast or Other)	Cohort 1: 8 Gy x 3 → Cohort 2: 17 Gy x 1		TOTAL
		Number of Patients	Number of Patients	
		6	6	12
		6	6*	12
TOTAL		12	12	24
* Breast or Other cancer patients only				

Expansion Phase

Disease	Randomize		Number of Randomized Patients
	Cohort 1: 8 Gy x 3	Cohort 2: 17 Gy x 1	
Melanoma	7	7	14
NSCLC	7	7	14
Pancreas	6	0	6*
Breast	3	3	6
Other	3	3	6

TOTAL	26	20	46
	* Pancreas patients are not randomized, they are assigned to 8 Gy x 3		

In the ***Expansion Phase***, patients will be stratified by disease site. If both fractionation regimens are safe, then we randomize patients. Otherwise, all patients will be enrolled on the single regimen determined to be safe. We will proceed to the Expansion phase once 12 patients have been treated in a given stratum in the Safety phase and the requisite amount of time for observing DLTs has elapsed; i.e. once 12 patients have been treated in “No Prior PD-1 (Pancreas, Breast, Other)” stratum, patients can be enrolled on the Pancreas, Breast and Other strata in the Expansion phase. Likewise, once 12 patients have been treated in “Progressed on the Prior PD-1 (Melanoma, NSCLC)” stratum in the Safety phase and the requisite amount of time for observing DLTs has elapsed, patients can be enrolled on the Pancreas, Breast and Other strata in the Expansion phase.

46 patients will be enrolled. Randomization will aid in the preliminary assessment of clinical response by avoiding selection bias. Accrual is expected to occur over 24 months or 3-4 subjects per month.

Radiation Therapy

All subjects will be immobilized in a custom designed device in the appropriate position to isolate the index lesion. Radiotherapy treatment planning using CT or PET/CT scans (with contrast, unless contraindicated) will be required to define the gross target volume (GTV) and planning target volume (CTV). The treatment planning PET/CT scan should be acquired with the subject in the same position and using the same immobilization device as for treatment. Treatment planning will be done using a 3D based CT treatment planning system. All tissues to be irradiated must be included in the CT scan. Planning CT scan will be done at \leq 5 mm intervals from encompassing the region of interest with sufficient margin for treatment planning.

Target Contouring

Gross Tumor Volume (GTV) is defined as all known gross disease encompassing the selected index lesion. The GTV will consist of the index lesion as visualized on CT and PET.

Internal Gross Tumor Volume (IGTV) is defined for mobile index lesions at the discretion of the treating physician. A 4-D CT scan may be acquired in order to account for the motion of the lesion during respiration. The IGTV will be defined as the union of the visualized index lesion on all gated CT data sets.

Planning Target Volume (PTV) will be defined as per the convention for photon beam radiotherapy. A 3-dimensional margin will be created on the GTV or IGTV (if available) to allow for daily set-up variance.

Normal Structures

Organ at risk volume (OAR) is contoured as visualized on the planning CT or MR scan. Planning PAR is the OAR expanded for setup uncertainty or organ motion. The physician will contour the OAR. The dosimetrist will create the PAR by expanding the OAR by 2-3 mm, depending on the situation.

Dose Fractionation and Specification

The prescription dose per fraction to the PTV will be 8 Gy x three fraction for Cohort 1 and 17 Gy per fraction x one fractions in Cohort 2. The total dose for Cohort 2 will be 24 Gy over 3 fractions.

Treatment Planning

Three-dimensional coplanar or non-coplanar beam arrangements will be custom designed for each case to deliver highly conformal prescription dose distributions. Non-opposing, noncoplanar beams are preferable.

Many of the patients on this trial will undergo SBRT. For these patients, standard protocols and constraints that have been developed in the Department of Radiation Oncology will be followed. For SBRT, typically, ≥ 10 beams of radiation will be used with roughly equal weighting. Generally, more beams are used for larger lesion sizes. When static beams are used, a minimum of 7 non-opposing beams should be used. For arc rotation techniques, a minimum of 340 degrees (cumulative for all beams) should be utilized. For arc rotation techniques, a minimum of 340 degrees (cumulative for all beams) should be utilized. In order to obtain acceptable coverage, field aperture size and shape should correspond nearly identically to the projection of the PTV along a beam's eye view (i.e., no additional "margin" for dose buildup at the edges of the blocks or MLC jaws beyond the PTV). The only exception should be when observing the minimum field dimension of 3.5 cm when treating small lesions. As such, prescription lines covering the PTV will typically be the 60-90% line (where the maximum dose is 100%); however, higher isodoses (hotspots) must be manipulated to occur within the target and not in adjacent normal tissue.

Dose Selection/Modification

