1.0 TRIAL SUMMARY

Abbreviated Title	RadVax™: Pembrolizumab & Hypofractionated Radiotherapy
Phase	Phase I
Clinical Indication	Metastatic cancers
Trial Type	Phase I cohort with randomized expansion phase
Type of control	N/A
Route of administration	i.v.
Trial Blinding	N/A
Treatment Groups	2 radiotherapy cohorts; 5 disease cohorts
Number of trial subjects	70
Estimated duration of trial	2 years
Duration of Participation	3 months

IRB #: 821403

UPCC#: 40914

Original Version: February 3, 2015

This document is a protocol for a human research study. This study is to be conducted according to US and international standards of Good Clinical Practice (FDA Title 21 part 312 and International Conference on Harmonization guidelines), applicable government regulations and Institutional research policies and procedures.

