5.3 Stratification and Randomization

During the Safety Phase of this study, patients will be stratified on the basis of having received prior immunotherapy (see Table 3). During the Expansion Phase, patients will be stratified by disease site. If both fractionation regimens are safe, then we will randomize patients. Otherwise, all patients will be enrolled on the single regimen determined to be safe. Randomization will aid in the preliminary assessment of clinical response by avoiding selection bias. The randomization procedure is described in the Statistical Section.

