8.0 STATISTICAL ANALYSIS PLAN

This is a stratified phase I trial with 2 phases: a safety phase and an expansion phase.

Safety Phase: Pembrolizumab is fixed. Two radiotherapy fractionation schedules are tested: 8 Gy x 3 and 17 Gy x 1. Patients are stratified by prior PD-1 therapy. 24 patients will be enrolled, 12 per stratum and 6 per fractionation cohort.

Table 11

	Progressed on Prior PD-1 (Melanoma or NSCLC)	Cohort 1: 8 Gy x 3 Number of Patients	Cohort 2: 17 Gy x 1 Number of Patients	TOTAL
		6	6	

May 3, 2017

Confidential  Limited Access

Stratify	No Prior PD-1 (Pancreas, Breast or Other cancers)	6	6*	12
	TOTAL	12	12	24
	* Breast or Other cancer patients only			

Safety Phase Decision-making: Dose limiting toxicity (DLT) is defined in Sections 2.1 and 5.2. The regimen is considered safe if 0-1 DLTs are observed in 6 patients within a stratum. Stop if 2+ DLT at any time. If 2+ DLT in Cohort 1, then Cohort 2 will still be tested. Cohort 1 → Cohort 2 is not an escalation of dose.

Expansion Phase: Patients are now stratified by disease site.

- If both fractionation regimens are considered safe for both prior PD-1 therapy strata, then we will randomize patients. Randomization will aid in our preliminary assessment of clinical response by avoiding selection bias. Although unlikely, if only one of the fractionation regimens is considered safe for both prior PD-1 therapy strata, then all patients will be enrolled on the fractionation regimen which was determined to be safe.

Table 12

Disease	Randomize		Number of Randomized Patients
	Cohort 1: 8 Gy x 3 Number of Patients	Cohort 2: 17 Gy x 1 Number of Patients	
Melanoma	7	7	14
NSCLC	7	7	14
Pancreas	6	0	6*
Breast	3	3	6
Other cancers	3	3	6
TOTAL	26	20	46
	* Pancreas patients are not randomized, they are assigned to 8 Gy x 3		

Expansion Phase Decision-making: We will first evaluate response rate by fractionation cohort. We will pool all disease sites. This is a global assessment of RADVAX™ by fractionation cohort. Of 38 patients in cohort 1, 26 (68%) and of 32 patients in cohort 2, 20 (63%) will have been randomized to treatment in the expansion phase, which strengthens any comparative conclusions, although preliminary. Immune PD markers will also be examined by fractionation cohort.

Table 13

	Cohort 1: 8 Gy x 3 Number of Patients	Cohort 2: 17 Gy x 1 Number of Patients	STUDY TOTAL
Safety phase	12	12	24
Expansion phase	26	20	46
TOTAL	38	32	70

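### No stated rule uses the Safety Phase order, yet its 24 unrandomised patients, plus 6 assigned pancreas patients counted as randomised, enter the response comparison of the two radiotherapy regimens

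*Combined protocol and SAP*

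**What the plan says.** - **Where randomisation applies.** Section 1.0 describes the trial as a "Phase I cohort with randomized expansion phase". Section 8.0 makes this conditional: "If both fractionation regimens are considered safe for both prior PD-1 therapy strata, then we will randomize patients". For the Safety Phase, Section 5.3 mentions stratification only: "During the Safety Phase of this study, patients will be stratified on the basis of having received prior immunotherapy".
- **Safety Phase layout.** Section 5.2: "24 patients will be enrolled, 12 per stratum and 6 per fractionation cohort within each stratum". Table 3 joins the two cohorts with an arrow from Cohort 1 to Cohort 2. It places the word randomise over the Expansion Phase table only.
- **Role of the order.** Section 5.2: "If 2+ DLT are observed in Cohort 1 in a stratum, then Cohort 2 within that stratum will still be tested". Section 8.0: "Cohort 1 → Cohort 2 is not an escalation of dose". The safety criterion is applied cell by cell: "The regimen is considered safe if 0-1 DLTs are observed in 6 patients within a stratum". Under Section 5.2, a stratum moves to expansion only after its 12 patients have been treated and the time for observing DLTs has passed.
- **Use of the data.** Section 8.0 evaluates response by fractionation cohort with both phases and all disease sites pooled, 38 v 32 (Tables 13 and 14). It says that 26 of 38 (68%) and 20 of 32 (63%) will have been randomised, "which strengthens any comparative conclusions, although preliminary".
- **Pancreas.** The footnote to Table 12 says the 6 Expansion Phase pancreas patients are assigned to Cohort 1 without randomisation. The footnotes to Tables 3 and 11 restrict Cohort 2 in the stratum without prior PD-1 therapy to breast and other cancers.

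**The concern.** Filling cohorts in sequence usually has a purpose: the first result decides whether the second cohort opens. Here no stated DLT rule works that way, and the order does not bring expansion forward either. What the order does do is tie regimen to enrolment period for 24 patients, who then count in the comparison of regimens.

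The plan gives avoiding selection bias as its reason for randomising the Expansion Phase. The same reason applies to Safety Phase patients who could receive either regimen. The plan also overstates how much of Cohort 1 is randomised, so a reader would give the pooled comparison more weight than it can bear.

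**Working it through.** **1. The plan's own shares.** 26/38 = 68.4% and 20/32 = 62.5%, so the stated 68% and 63% reproduce as arithmetic. The exact intervals in Table 14 also reproduce in all ten rows.

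**2. Shares after applying the Table 12 footnote.** Of the 26 Expansion Phase patients in Cohort 1, 6 are assigned pancreas patients, which leaves 26 − 6 = 20 randomised.

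| | Cohort 1 | Cohort 2 | Total |
|---|---|---|---|
| Safety Phase, not randomised | 12 | 12 | 24 (34%) |
| Expansion pancreas, assigned | 6 | 0 | 6 (9%) |
| Randomised | 20/38 (53%) | 20/32 (63%) | 40/70 (57%) |
| Not randomised | 18/38 (47%) | 12/32 (38%) | 30/70 (43%) |

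**3. How many Safety Phase patients could be randomised.** The 12 melanoma/NSCLC patients fit 6:6 with no change to the cells, giving 26 v 26 (52/70 = 74%). In the other stratum, pancreas patients can take only the 6 Cohort 1 places. With k pancreas patients, breast and other patients must split (6 − k):6 to keep 6 per cell. Table 15 expects k = 4 but does not require it.
- k = 0: 6:6, total 32 v 32.
- k = 4: 2:6, total 28 v 32 (60/70 = 86%).
- k = 6: no Cohort 1 places remain, so nothing can be randomised and the total stays at 26 v 26.

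**4. Precision of the difference in response rates.** The plan gives no response rate for this purpose, so I assume 25% in both arms. I also assume that both regimens pass in both strata, so that the Expansion Phase is randomised. For an analysis within randomisation groups, half-width = 1.96 × √(0.25 × 0.75 / W), where W is the sum of n₁n₂/(n₁ + n₂) over groups.
- Expansion only: the 7 v 7, 7 v 7, 3 v 3 and 3 v 3 groups give W = 3.5 + 3.5 + 1.5 + 1.5 = 10. Half-width 26.8 points.
- Adding melanoma/NSCLC Safety Phase patients 6 v 6: W = 10 + 3 = 13. Half-width 23.5 points.
- Adding breast/other 2 v 6 (k = 4): W = 13 + 12/8 = 14.5. Half-width 22.3 points.
- Adding breast/other 6 v 6 instead (k = 0): W = 13 + 3 = 16. Half-width 21.2 points.
- For reference, the crude pooled 38 v 32: W = 38 × 32/70 = 17.4. Half-width 20.4 points, but 30 of those patients are unrandomised.

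**5. Possible size of the bias.** Suppose, as an illustration, that Safety Phase patients in one cohort have an underlying response rate 20 points different from those in the other, for reasons unrelated to regimen. The pooled difference moves by 20 × 12/38 = 6.3 points if Cohort 1 carries the shift, or 20 × 12/32 = 7.5 points if Cohort 2 does.

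**6. Disease mix.** With 4 Safety and 6 Expansion pancreas patients, Cohort 1 would hold 10/38 (26%) pancreas patients and Cohort 2 none. Pooling all disease sites therefore mixes regimen with disease as well as with time.

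**The case against.** The best argument for the plan is caution. Section 4.2.3 says there are no clinical safety data for the combination. Filling one cohort first lets early toxicity be noticed before the second opens. Section 5.9 allows the trial to stop for adverse reactions, and grade 3 or higher events go to the monitoring committee within 5 days. That stands as an informal benefit, so a reader should not infer that the sequence brings no gain. The supportable statement is that no stated DLT or expansion rule uses it. The DLT rule works cell by cell, and 1:1 allocation would fill each cell more slowly, not faster.

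Three other stronger readings are tempting and are not supported:
- **That the primary DLT result is compromised.** Each cell is judged against a fixed threshold of 0-1 DLT in 6, and no test of DLTs between regimens is planned.
- **That investigators choose the regimen.** The arrow in Table 3 suggests sequential filling. The figure in Section 2.1 and the diagram in Section 2.2 were not available in the text I read. If either shows a Safety Phase allocation method, the point about order must be revisited.
- **That the randomised set could reach 30 v 30 with the expected case mix.** With 4 pancreas patients and 6 per cell, it is 28 v 32.

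It is also fair to say that response is a secondary objective, that Table 14 gives separate intervals and no difference, test or power, and that the plan discloses partial randomisation and calls its conclusions preliminary. All of this limits the severity. It does not excuse the 68%, because the disclosure itself is wrong.

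**Conclusion.** The point holds in a limited form. The Safety Phase is not described as randomised, no stated rule depends on its order, and its 24 patients (34%) enter the regimen response assessment with regimen mixed with calendar time. The count of randomised patients in Cohort 1 contradicts the plan's own footnote: it is 20/38 (53%), and 30/70 (43%) are unrandomised overall. This second part needs no assumption and is the firmer of the two.

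The gain from randomising is real but modest: 26.8 to 23.5 points with the melanoma/NSCLC patients, or 22.3 if breast and other patients are added with 4 pancreas patients. These figures rest on an assumed 25% response rate in both arms and on both regimens passing in both strata. Even the narrower interval is too wide to choose a regimen. Severity is low to moderate.

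**What to change.** 1. In Sections 5.2, 5.3 and 8.0, randomise the 12 melanoma/NSCLC Safety Phase patients 6:6 between regimens, with 6 per cell and the DLT rule unchanged, or state why not. Say how patients are allocated if one cell stops early; those entered afterwards in that stratum would not count as randomised.
2. Randomise breast and other Safety Phase patients only over places not reserved for pancreas patients, with the number reserved fixed in advance. Otherwise leave them assigned and say so.
3. In Section 8.0, replace 26/38 (68%) with 20/38 (53%), and relabel the column of Table 12 that totals 46 as randomised, since only 40 are.
4. Base the regimen comparison on randomised patients from both phases, analysed within the groups in which they were randomised. Report the pooled 38 v 32 as descriptive.

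The cost is protocol wording and an earlier start to the randomisation list, with no extra patients. The downside is that Cohort 1 toxicity is no longer seen informally before Cohort 2 opens. If the Safety Phase has already enrolled, items 1 and 2 are no longer possible. Items 3 and 4 still apply, with 20 v 20 as the randomised comparison.

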2.0 TRIAL DESIGN

2.1 Trial Design

This is a Phase I cohort study of a fixed dose of Pembrolizumab in combination with two distinct regimens of hypofractionated radiotherapy. There will be five groups of patient diagnoses:

- Metastatic melanoma patients who have progressed while on PD-1 or PDL-1 therapy
- Metastatic NSCLC patients who have progressed while on PD-1 or PDL-1 therapy
- Metastatic & locally advanced pancreatic cancer patients
- Metastatic Breast cancer patients
- Other metastatic cancer patients

Pembrolizumab will be administered at a dose of 200 mg every 3 weeks beginning 7 days (+/- 3 days) prior to the first fraction of hypofractionated radiation and will continue for a total of 6 cycles. In the initial **Safety Phase**, there will be two cohorts of patients based upon the radiotherapy dose delivered to the index metastatic lesion in the lung, liver, bone or soft tissue:

Cohort 1: 8 Gy x 3 to the index lesion

[figure not shown]
Cohort 2: 17 Gy x 1 to the index lesion*

*Subjects with locally advanced pancreatic cancer will be enrolled only in the 8 Gy x 3 cohort.

Patients are stratified by prior PD-1 therapy. 24 patients will be enrolled, 12 per stratum and 6 per fractionation cohort. Standard safety decision-making will be used. The regimen is safe if 0-1 dose-limiting toxicities (DLT) in 6 patients (3 from each strata). Enrollment in a cohort will stop if 2+ DLT are observed within a cohort at any time during the safety phase. If 2+ DLT are observed in Cohort 1, then Cohort 2 will still be tested. Cohort 1 → Cohort 2 is **not** an escalation of dose. DLT is defined as any Grade 3 or higher non-hematological toxicity and any Grade 4 hematological toxicity that is probably, possibly or definitely related to the combination of Pembrolizumab and hypofractionated radiotherapy. The window in which DLTs will be recorded is from the first Pembrolizumab infusion to 35 days after the last radiation fraction.

In the **Expansion Phase**, patients will be stratified by disease site. If both fractionation regimens are safe, then we randomize patients. Otherwise, all patients will be enrolled on the single regimen determined to be safe. 46 patients will be enrolled. Randomization will aid in the preliminary assessment of clinical response by avoiding selection bias. Accrual is expected to occur over 24 months or 3-4 subjects per month.

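### Sections 2.1 and 5.2 apply the DLT limit at different levels, so one DLT in each stratum stops a regimen under 2.1 and clears it under 5.2; 5.2 also names the wrong diseases in an expansion gate.

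*Combined protocol and SAP*

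**What the plan says.** **Safety rule.** Section 2.1 states: "The regimen is safe if 0-1 dose-limiting toxicities (DLT) in 6 patients (3 from each strata"; and for stopping: "Enrollment in a cohort will stop if 2+ DLT are observed within a cohort at any time during the safety phase". It gives the size as "24 patients will be enrolled, 12 per stratum and 6 per fractionation cohort". It is also the only section that defines the DLT window: "The window in which DLTs will be recorded is from the first Pembrolizumab infusion to 35 days after the last radiation fraction".

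Section 5.2 calls a regimen safe if no more than one DLT "are observed in 6 patients within a cohort within a stratum", and adds: "Enrollment in a cohort within a stratum will stop if 2+ DLT are observed within that cohort at any time during the safety phase". Table 3 (section 5.2) and Table 11 (section 8.0) both show 6 patients in each of the four cohort-by-stratum cells.

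Two other sections restate the rule less fully. Section 4.2.3, which defines the primary endpoint, counts 0 or 1 DLTs in 6 patients per radiation dose cohort and does not mention strata. Section 8.0 counts 0-1 DLTs in 6 patients per stratum without naming the cohort, and its stop instruction names no level.

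**Opening expansion.** Section 5.2 gives a general rule, "We will proceed to the Expansion phase once 12 patients have been treated in a given stratum in the Safety phase", once the DLT observation time has also passed. Two worked cases follow. The first ties pancreas, breast and other cancers to the stratum with no prior PD-1 therapy. The second, introduced by the word Likewise, is about the melanoma/NSCLC stratum but ends "DLTs has elapsed, patients can be enrolled on the Pancreas, Breast and Other strata in the Expansion phase".

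**Allocation in expansion.** Section 5.2 randomizes if both regimens are safe and otherwise uses the single safe regimen. Section 8.0 randomizes only if both regimens are safe in both strata, and uses a single regimen if only one is safe in both.

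**The concern.** These sentences decide when a cohort stops, which disease groups may enter expansion, and on which regimen. If 2.1 and 5.2 give different answers to the same DLT counts, the primary conclusion depends on which section the study team opened. Settling that after DLTs have been seen would look data-driven.

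Section 2.1 cannot be set aside as a loose summary. Section 8.0 refers to both 2.1 and 5.2 for the DLT definition, and anyone applying 5.2's observation time has to go to 2.1 for the 35 days, where the other stopping rule stands.

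The wrong disease list matters because it sits in an enrollment gate. Read literally, it opens pancreas, breast and other cancers on another stratum's safety data.

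**Working it through.** **1. Sample sizes.** Under 5.2: 2 regimens x 2 strata x 6 = 24, which reproduces the stated safety-phase total. Under 2.1's layout: 2 regimens x (3 + 3) = 12, which does not match the 24 that 2.1 itself states. Expansion: 14 + 14 + 6 + 6 + 6 = 46, of which melanoma and NSCLC are 14 + 14 = 28. Whole trial: 24 + 46 = 70, as stated.

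**2. Where the rules part.** Take one regimen. With 0 or 1 DLT in total, both rules pass it. With 2 or more in one stratum, 2.1 stops it and 5.2 stops it in that stratum. With exactly one DLT in each stratum, 2.1 counts two in the cohort and stops; 5.2 counts one in each cell and passes both. This 1+1 split is the only one in which 5.2 clears the regimen in both strata while 2.1 stops it.

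**3. How often.** No DLT rate is given. Assume a rate p of 5, 10 or 15%, equal and independent across patients.

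| Quantity | p = 5% | p = 10% | p = 15% |
|---|---|---|---|
| P(1 DLT in 6) = 6p(1-p)^5 | 0.2321 | 0.3543 | 0.3993 |
| One in each stratum: x = square of the above | 0.0539 | 0.1255 | 0.1595 |
| On at least one of two regimens: 1-(1-x)^2 | 0.105 | 0.235 | 0.294 |
| s = P(at most 1 in 6) | 0.9672 | 0.8857 | 0.7765 |
| 5.2 clears the regimen in both strata: s^2 | 0.9355 | 0.7845 | 0.6029 |
| 2.1's limit applied to 12: P(at most 1 in 12) | 0.8816 | 0.6590 | 0.4435 |
| 3 per stratum, one in each: [3p(1-p)^2]^2 | 0.0183 | 0.0590 | 0.1057 |

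As a check, the fifth row minus the sixth equals x, up to rounding.

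**4. Opening against allocation.** Under 5.2 a stratum can open on its own results, but 8.0 cannot say whether it is randomized until the other stratum reads out. The chance that a given stratum clears both regimens and the other does not is s^2(1-s^2) = 0.0603 / 0.1690 / 0.2394.

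Section 8.0 alone has no branch when neither regimen is safe in both strata but at least one cell passes. Of the 16 pass/fail patterns of four cells, 1 has both regimens safe in both strata, 6 have exactly one, 8 are mixed in this way, and 1 has no safe cell. The mixed patterns have probability (1-s^2)^2 - (1-s)^4 = 0.0042 / 0.0463 / 0.1552.

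**5. The 12-treated condition.** A cell that stops at 2 DLTs among its first 5 patients never reaches 6, so its stratum never reaches 12. If every DLT were known before the next patient entered, the chance for a stratum would be 1-(1-P(2 or more in 5))^2 = 0.0447 / 0.1563 / 0.3024. This is an upper bound, because the window runs to Day 8 + 35 = 43 (17 Gy x 1) or Day 12 + 35 = 47 (8 Gy x 3).

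**The case against.** The strongest reply is that most of this has one sensible reading. The 24-patient total, Tables 3 and 11, and 8.0's per-stratum count all point to 5.2. The word Likewise signals a parallel, so the disease list is a slip that no one would follow. Every percentage rests on an assumed DLT rate, and the larger set combines 2.1's stop rule with 5.2's 6-per-cell layout; on 2.1's own layout the figures are smaller. Moving to 5.2 also adopts the more permissive limit, since two DLTs in 12 would then pass if they fall one in each stratum.

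Much of this stands and limits the point. A reader might infer that nothing in the protocol opens expansion for melanoma and NSCLC. That goes too far: the general rule in 5.2 covers any stratum, and Tables 3 and 12 allot each of these diseases 14 places. A reader might also infer that mixed safety results have no rule anywhere. That is true only of 8.0; 5.2's fallback, read stratum by stratum, lets a stratum proceed on whichever regimen it has cleared. Nor does 8.0 forbid staggered opening, so the timing point is a mismatch of levels and not a contradiction.

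The reply does not remove the stopping conflict. Two sections give opposite instructions for the same counts, and that holds at any DLT rate. Section 4.2.3 does not settle it: six patients per radiation cohort could mean 2.1's pooled six or 5.2's cell, and a radiation cohort holds 12 in Tables 3 and 11.

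**Conclusion.** The main point holds on the text. On one DLT per stratum, 2.1 stops a regimen that 5.2 clears, and that decision is the primary endpoint. At assumed DLT rates of 5 / 10 / 15%, this arises with probability 5.4 / 13 / 16% per regimen with 6 per cell, or 1.8 / 5.9 / 11% with 3 per stratum. The rates show the scale only. Section 2.1 also disagrees with its own total of 24. The weight of the document favours 5.2. This needs correcting before DLT data exist.

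The wrong disease list in 5.2 is a plain copy error with clear intent, but it stands in the gate for 28 of 46 expansion places and should be corrected with the first point.

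The different levels used by 5.2 and 8.0 are a lesser matter: 6 / 17 / 24% for a given stratum clearing both regimens while the other does not, on the same assumptions. The 12-treated wording needs only clarification, since both 5.2 and 8.0 plainly intend expansion to continue on the safe regimen.

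**What to change.** 1. State one rule in 2.1, 4.2.3, 5.2 and 8.0: a regimen is safe with 0-1 DLT in 6 patients in a cohort within a stratum, and stopping at 2 or more DLTs applies at that same level. Delete the 3-per-stratum wording from 2.1. Record that this passes one DLT in each stratum (2 in 12), so that the sponsor accepts the more permissive limit knowingly.
2. In 5.2, end the sentence on the melanoma/NSCLC safety stratum with the melanoma and NSCLC strata.
3. Use the same level, per stratum or both strata, for opening expansion in 5.2 and for allocation in 8.0, and have 8.0 state what happens when neither regimen is safe in both strata.
4. In 5.2, replace the 12-treated condition with: once each cohort in the stratum has completed or stopped and the DLT window of 2.1 has elapsed.

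**Cost.** Wording only, with no extra patients. Under item 3, a both-strata gate makes the faster stratum wait. Taking the time for each stratum to accrue 12 patients as gamma distributed, with the stated 3-4 patients per month arriving at random and DLT pauses ignored, the mean wait is about 1.9 to 2.6 months if arrivals split equally between strata and 4.6 to 6.1 months at a 2:1 split (both splits are assumptions). A per-stratum gate avoids the wait but can leave the strata on different regimens, which weakens the pooled comparison of 38 with 32 patients.
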